15.8.1 Concomitant treatment in the event of relevant AEs

Depending on the severity and type of the AEs, the following treatments are suggested treatments and may be changed at the discretion of the responsible physician.

Allergic reaction

Treatment with best standard treatment option according to the local investigator's site circumstances (e.g. antihistamines, glucocorticoids). The investigator will provide all the necessary emergency equipment at the study centre and specially trained staff to handle emergency events during this study (anaphylactic shock).

15.9 Appropriateness of measurements

All methods used for safety assessments are standard methods for which reliability, accuracy and relevance have been documented (e. g. pregnancy test).

15.9.1 Clinical laboratory parameters

In this study no clinical laboratory parameters will be routinely determined.

15.9.2 Clinical parameters

Body weight and height will be measured with commercial instruments. Lice assessment will be done according to the instructions given in chapter 15.5.6. The study staff will be trained for combing and determine the live stages of lice.

15.10 Handling and documentation of clinical data

The Principal Investigator has to ensure that all data required according to this protocol and not mentioned as exception in the following will be entered promptly in the CRF.

The following variables will be documented in the patient's records ore in raw data sheets prior to transfer in the CRF. A paper CRF will be used in this study.

Category	Variables	Source	Details
Identification	Patient number, random number, screening number	Screening/enrolment log, patient file, random list	
Demographic data	Ethnic origin, gender, age, height, weight, participation in another clinical trial within 4 weeks,	Patient file or raw data sheet	
	Childbearing potential, pregnancy, breastfeeding, contraceptive method, result pregnancy test	Patient file or raw data sheet	Woman only
Description of study condition	Confirmation of head lice infestation, severity of head lice infestation, hair length, number of living head lice, live stage of lice	Patient file or raw data sheet	
Randomisation	Check inclusion/exclusion criteria	Patient file or raw data sheet	
	Randomisation	Enrolment log, Patient file	
	Reasons for non- inclusion into treatment	Patient file	
Concomitant medication	Trade name, indication, route, frequency, total daily dose, start date, stop date, ongoing	Patient file or raw data sheet	
Medical history	Disease, date of diagnosis, stop date, ongoing	Patient file or raw data sheet	Relevant findings
Safety	Local tolerability	Patient file or raw data sheet	
	Global tolerability by patient	Raw data sheet	

Category	Variables	Source	Details
	Global tolerability by investigator	Patient file or raw data sheet	prior to patient's assessment
	Skin irritation	Patient file or raw data sheet	
	Eyes irritation	Raw data sheet	
	Satisfaction with the esthetical effect	Raw data sheet	
	Combing by patient	Patient file or raw data sheet	
Administration	Amount of study medication, date of administration, start time, stop time	Drug dispensing log	
Completion	Date of completion, type of termination, reason for premature termination, date of premature termination, health state	Patient file	
AE	Description, start date/time, stop date/time, seriousness, severity, causal relationship, expectedness, action taken regarding study drug, action taken regarding subject	Patient file and raw data sheet	
PTSS	Description, start date/time, stop date/time, severity, action taken regarding subject, deterioration to AE	Patient file and raw data sheet	

All data primarily documented on patient file, raw data sheet, or several logs will be transferred later to the CRF.

For the purpose of quality control, a member of the study team will check data on the CRF's for formal correctness, completeness and legibility of the entries.

Entries on the CRF's must be made with a ball-point pen and must be legible. Pencils and correction fluids are not to be used. If corrections are necessary, they will be entered by a member of the study team in the following manner: the wrong CRF entry will be crossed out; however, it must remain legible, and the correct entry will be placed in the correction field (if applicable) or next to the wrong entry. Corrections will be initialled and dated.

A sample CRF is provided in the Trial Master File. The CRF will be supplied by the CRO. The originals are to be returned to the Sponsor. One copy will remain at the Investigator's site.

The CRFs for any subject leaving the study should be completed at the time when study participation is terminated. CRFs should accurately reflect data contained in subject's records (i.e. source documents).

15.11 Clinical data management

The data management department of CardioSec GmbH will create a database, which reflects the final version of the CRF. Upon receipt of CRF's in data management, the information from the CRF's will be entered in the validated database according to the corresponding SOP's. Edit checks on completeness, correctness, plausibility (such as range checks, cross-checks) will be performed. All identified discrepancies will be queried by the data manager(s) using data discrepancy forms.

The completed data discrepancy forms will become part of the CRF and, therefore, the original data discrepancy form will be filed with the original CRF; copies must be archived at the centre. All changes to the database will be tracked (audit trail).

Details on data management procedures will be fixed in a detailed data management plan.

16 Biostatistics

The biostatistics department of ACOMED statistik will perform the analysis of the study according to its SOPs.

16.1 Populations for analyses

Safety population (SAF):

All enrolled subjects who administered the investigational product, independently of the duration of treatment.

Per-protocol population (PP):

All enrolled subjects, who show no major protocol deviations (to be defined before database lock). All subjects who provide valuable data.

16.2 Description

Descriptive statistics of all endpoint variables will be tabulated (continuously scaled variables: mean, standard deviation, median, min, max, categorically scaled variables: counts and percentages) by visit and treatment.

16.3 Analysis of primary objective

The cure rate p is defined as proportion of patients who will be found to be cured at evaluation follow-up-visit V04 among all patients received any treatment at visit V01.

The aim of the study is to show superiority for the cure rate of investigated treatment p_T versus a predefined limit of 70%. This limit refers to cure rates found for several formulations which are accepted for the intended use.

The following null hypothesis will be tested:

 $H_{0,prim}$: $p_T = 70\%$

If $p_T > 70\%$ and the null hypothesis is rejected by a two sided, one sample χ^2 -test at 0.05 level, superiority will be concluded.

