16.5 Determination of sample size

The design of the trial including the number of subjects is adapted from a previous trial performed with Silcap shampoo [24] and based on statistical calculation.

According to [21], a 90% cure rate can be expected for the study medication. In general, a cure rate of 70% can be assumed to a minimal accepted cure rate. The primary objective refers to superiority of cure rate vs. this limit. A sample size of 42 is required for a one group χ^2 -test comparing cure rate of 90% with a fixed limit of 70% (two sided test; alpha-level of 0,05; power=90%; software nQuery advisor 7.0; power=80%: sample size=34).

For the reference group, the identical sample size is used. Assuming 10% drop outs and a 5% rate for re-infestation, the sample size has to be multiplied by 1.1×1.05 leading to approximately 50 cases (exactly: 49 cases which have been rounded up to 50 cases).

The sample size is also applicable to show secondary objectives 3 and 4, if following cure rates are assumed:

Superiority: 60% vs 90% (90% power), 65% vs. 90% (80% power).

Non inferiority (margin: -7,5%): 70% vs. 90% (90% power).

¹ For practical considerations: Note that the half width of one sided 0.025 one sided CI and two sided 0.05 two sided CI are equal.

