16.8 Quality control for statistical procedures

The statistical analysis will be conducted in compliance with the ICH E9 Note for Guidance on Statistical Principles for Clinical Trials (CPMP/ICH/363/96, 1998).

Quality control will be performed according to the SOPs of ACOMED statistik. Quality control includes checks of data, checks of calculations as well as formal checks of tables, listings and figures. All steps of quality control will be documented with signature of the reviewer and date of review.

17 Evaluation of efficacy parameters

The ITT population will be used for analysis of efficacy variables with exception of noninferiority, where PP population will be investigated.

The primary analysis will be repeated for PP population.

Missing values will not be imputed patients dropping out because of non-effective treatment will be counted as non-responders by study design.

Details of the analysis will be fixed in the Statistical Analysis Plan (SAP) which will be finalised before database lock.

18 Evaluation of safety parameter

For definition of safety set/population see section 16.1.

All analyses will be performed for the safety population. Due to the short treatment duration, the topical administration (associated with a low risk of systemic availability of pyrethrum or mineral oil) and comprehensive data on the safety profile of the active substance, laboratory safety tests will not be performed routinely.

Secondary parameters for tolerability and safety:

Local tolerability assessment (subjective	Burning, paraesthesia, pruritus at day 0 (0h, 1h), day 1, day 7 (0h, 1h) and day 10 p.a.
symptoms)	Frequencies and percentages (related to number of patients with information) will be given for each symptom.
Global tolerability	Patients will assess the overall treatment tolerability at day 10 p.a.
assessment (patient):	Frequencies and percentages (related to number of patients with

	information) will be given for each score as well as for the combined score "very good" / "good".
Global tolerability assessment (study staff):	The investigator will assess the overall treatment tolerability at day 10 p.a.
	Frequencies and percentages (related to number of patients with information) will be given for each score as well as for the combined score "very good" / "good".
Skin irritation	Secondary infection, erythema, excoriation of the skin at -1h (baseline assessment), day 0 (0h, 1h), day 1, day 7 (pre-treatment, 0h, 1h) and day 10 p.a.

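### The primary cure rate is defined on all treated patients in 16.3, but section 17 and the sample size in 16.5 imply that most drop-outs are removed, and the choice can reverse the 70% test

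*Protocol*

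**What the plan says.** Section 16.3 of the protocol gives the only explicit denominator. The cure rate is the "proportion of patients who will be found to be cured at evaluation follow-up-visit V04 among all patients received any treatment at visit V01", tested against 70% with a two-sided one-sample chi-square test at 0.05.

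Section 17 (Evaluation of efficacy parameters) adds two statements. On the analysis set: "The ITT population will be used for analysis of efficacy variables with exception of noninferiority, where PP population will be investigated". On missing data: "Missing values will not be imputed patients dropping out because of non-effective treatment will be counted as non-responders by study design". Sections 14.5 and 16.1 define a safety set and a per-protocol set; neither defines ITT.

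Section 16.5 assumes that "a 90% cure rate can be expected for the study medication" and that "a cure rate of 70% can be assumed to a minimal accepted cure rate". It reports 42 patients for 90% power and 34 for 80%. It then inflates: "Assuming 10% drop outs and a 5% rate for re-infestation, the sample size has to be multiplied by" 1.1 × 1.05, which gives 49, rounded to 50 per arm. The synopsis and 14.5 also say that patients who discontinue are replaced.

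Re-infestation is handled in more than one way. Sections 10.1 and 15.6 correct the cure rate for it, 15.5.6 calls any active infestation on day 10 a treatment failure, and 16.3 does not mention it.

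**The concern.** This is the trial's only primary test, and its denominator depends on which sentence the analyst follows. Under 16.3, a patient treated at V01 who is not seen at V04 cannot have been found cured, so the loss counts against the product whatever its reason. Section 17 singles out drop-outs for inefficacy as non-responders and leaves other missing values unimputed. The natural implication is that a patient lost for another reason is not a failure and is left out. The undefined ITT set does not decide between the two.

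Two things are at stake: whether the same data pass or fail against 70%, and whether the power given in 16.5 belongs to the analysis described in 16.3.

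**Working it through.** **Inputs.** From 16.5: p0 = 0.70, p1 = 0.90, 10% drop-out, 5% re-infestation, 50 per arm. From 16.3 and 16.5: two-sided alpha of 0.05.

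**The plan's own figure.** n = [(z₀.₉₇₅·√(p0·q0) + z_power·√(p1·q1)) / (p1 − p0)]²

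- 90% power: [(1.96 × 0.4583 + 1.2816 × 0.3) / 0.2]² = 41.1, so 42.
- 80% power: [(1.96 × 0.4583 + 0.8416 × 0.3) / 0.2]² = 33.1, so 34.
- Inflation: 42 × 1.1 × 1.05 = 48.5, so 49, rounded to 50.

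All stated figures reproduce.

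**Pass or fail.** z = (x − 0.7n) / √(0.21n), with success if z > 1.96. The smallest passing count is 42 of 50 (z = 2.16, p = 0.031) and 38 of 45 (z = 2.11, p = 0.034). Take 50 treated and 5 without V04 for reasons other than inefficacy:

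| Cured | On 50 (16.3) | On 45 (section 17 as implied) |
|---|---|---|
| 37 | 74.0%, p = 0.54, fail | 82.2%, p = 0.074, fail |
| 38 | 76.0%, p = 0.35, fail | 84.4%, p = 0.034, pass |
| 40 | 80.0%, p = 0.12, fail | 88.9%, p = 0.006, pass |
| 41 | 82.0%, p = 0.064, fail | 91.1%, p = 0.002, pass |
| 42 | 84.0%, p = 0.031, pass | 93.3%, p = 0.0006, pass |

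The two readings disagree for every count from 38 to 41. The plan's own assumptions point into that range: 0.90 × 0.90 = 0.81, and 0.81 × 50 = 40.5.

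**Power.** Exact binomial probability of reaching the smallest passing count, assuming 90% cure among assessed patients. Where drop-outs count as not cured, the all-treated rate is 0.90 × (1 − drop-out).

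| Situation | n | Rate | Count needed | Power |
|---|---|---|---|---|
| 16.3, no drop-out | 50 | 0.900 | 42 | 94% |
| 16.3, 2% unreplaced | 50 | 0.882 | 42 | 87% |
| 16.3, 5% unreplaced | 50 | 0.855 | 42 | 70% |
| 16.3, 10% unreplaced | 50 | 0.810 | 42 | 37% |
| 16.3, replaced to 50 completers | 55 | 0.90 × 50/55 = 0.818 | 46 | 45% |
| 16.3, replaced to 50 completers | 56 | 0.90 × 50/56 = 0.804 | 46 | 45% |
| Drop-outs removed | 45 | 0.900 | 38 | 92% |

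If 90% is already a rate among all treated patients, the first row applies (94%), and no inflation for drop-outs would be needed.

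**The case against.** Sections 16.3 and 17 can be read together. A patient not seen at V04 was not found to be cured, so nothing has to be imputed, and the sentence on inefficacy drop-outs is merely redundant. Section 17 states no denominator, and 16.5 is a planning allowance, not an analysis rule. Section 17 also sends details to a SAP. Part of this stands: only the 16.3 denominator is explicit, and the other reading is inferred. But the reconciliation makes the inefficacy clause pointless and still leaves the 16.5 inflation without a reason. Detail may go to the SAP; conflicting statements about the primary endpoint should be resolved in the protocol.

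A reader might infer three incompatible denominators. The documents do not support that. What section 17 and 16.5 imply about drop-outs is nearly the same, so the conflict is between counting all treated patients and removing most drop-outs.

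A reader might also take 37% as the power of this trial. That figure assumes drop-outs are not replaced, whereas the protocol replaces them, and it assumes that the 90% is a rate among assessed patients. The study behind the 90% is not at hand, so the second assumption cannot be checked.

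**Conclusion.** The inconsistency is real and affects the only primary test. At the planned 10% drop-out, if none is for inefficacy, the result reverses for 38 to 41 cured out of 50 treated. The arithmetic in 16.5 is correct, but its power belongs to an analysis with drop-outs removed.

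Under 16.3 as written, and with 90% taken as the rate among assessed patients, power ranges from 94% with no drop-out to 37% at 10% unreplaced drop-out, and is about 45% with replacement to 50 completers. If the 90% is an all-treated rate, there is no power shortfall, but the drop-out inflation then contradicts it. The pass/fail conflict does not depend on what the 90% means.

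**What to change.** - **16.1:** define ITT as all randomised patients treated at V01, analysed in the assigned arm, with patients who were later replaced kept in.
- **17:** state that no V04 lice assessment, for any reason, counts as not cured, in line with 16.3. Make the complete-case rate a named sensitivity analysis.
- **15.5.6, 15.6 and 16.3:** reconcile these so that one rule says how day-10 re-infestations enter the numerator and the denominator. Without it the endpoint stays ambiguous after the other edits.
- **16.5:** say which patients the 90% refers to, and restate the power for the chosen rule over 0–10% drop-out, allowing for replacement.

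The cost is a few sentences, a more conservative cure rate and a less favourable stated power. The edits do not themselves add patients, but keeping 50 per arm means accepting the restated power. On the least favourable assumption (all-treated rate 0.81), the formula in the working gives 162.2, so about 163 per arm for 90% power. The sponsor should see that figure before choosing the rule.

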16.4 Analysis of secondary objectives

The reference product will be tested in the same way.

Regarding difference of cure rates of test and reference product p_T - p_R , following hypotheses will be tested:

Superiority p_T vs p_R:

 $H_{0,sup}: p_T - p_R = 0.$

If $p_T - p_R > 0\%$ and the null hypothesis is rejected by a two sided, two sample χ^2 -test at 0.05 level, superiority of test product will be concluded.

According ICH guideline "Points to consider on switching between superiority and non-inferiority" [23] it is allowed to assess non-inferiority in addition to superiority if superiority cannot be shown. A non-inferiority margin has to be predefined. Moreover, no correction in terms of multiplicity is necessary. As non-inferiority margin δ , a 7.5% worse cure rate will be regarded as clinically not relevant.

The following null-hypothesis will be tested on α -level of 0.025¹.

 $H_{0,NI}$: p_T - p_R < δ , whereby δ = -7.5%

The lower, one sided 97.5% confidence interval of difference p_T - p_R will be used for the test. If $H_{0,NI}$ will be rejected, non-inferiority will be shown.

The difference of cure rates p_T - p_R as well the cure rates p_T and p_R will be presented with two sided 95% confidence interval.

The confidence interval for the difference in cure rates is calculated by SAS procedure PROC FREQ using statistic option RISKDIFF.

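### The non-inferiority decision rests on a RISKDIFF interval with no method named; read as Wald, it does not hold 2.5% when cure rates are high

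*Protocol*

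**What the plan says.** Protocol section 16.4 tests superiority of the test product over the reference first and falls back on non-inferiority if superiority is not shown. The margin is absolute, -7.5 points on p_T - p_R, justified by the statement that "a 7.5% worse cure rate will be regarded as clinically not relevant". The level is 0.025 and the decision is read directly off a confidence limit: "The lower, one sided 97.5% confidence interval of difference p_T - p_R will be used for the test". The same section then fixes the computation: "The confidence interval for the difference in cure rates is calculated by SAS procedure PROC FREQ using statistic option RISKDIFF". No suboption and no interval method is given.

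A footnote to the test adds: "Note that the half width of one sided 0.025 one sided CI and two sided 0.05 two sided CI are equal". Section 16.5 says of the test product that "a 90% cure rate can be expected for the study medication" and states the power for this comparison as "Non inferiority (margin: -7,5%): 70% vs. 90% (90% power"). Chapter 17 assigns non-inferiority to the per-protocol population. Section 16.6 and chapter 17 leave further detail to a SAP that is not at hand.

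**The concern.** RISKDIFF names an option, not a method, and several interval methods can be obtained under it. For a descriptive table that would matter little. Here the lower limit is the test, so the choice of method decides whether non-inferiority is declared.

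The reading closest to the text is the plain asymptotic (Wald) interval. Its standard error is estimated from the observed proportions, so it shrinks as those proportions approach 100% and is zero if every patient in both arms is cured. With about 50 patients per arm and high cure rates the lower limit then sits too close to the point estimate. Non-inferiority would be declared somewhat too often, and the reported 95% interval for the difference would look more precise than it is.

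The fallback structure adds to this. Non-inferiority is needed when superiority has failed, which is most likely when the two arms are close. If the test product performs near its expected 90%, close arms mean a high reference rate as well.

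**Working it through.** **Inputs.** From section 16.5: 42 evaluable patients per arm ("A sample size of 42 is required for a one group" sample test against 70%), inflated to 50. From section 16.4: margin -0.075, one-sided 0.025. From chapter 17: per-protocol set. Arms are therefore taken as equal, with 42 to 50 patients each.

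**The plan's own figures reproduce.**
- One-sample test, 90% against 70%: n = [(1.96·√0.21 + 1.2816·√0.09)/0.20]² = 41.1, so 42.
- Inflation: 42 × 1.1 × 1.05 = 48.5, so 49, rounded up to 50.
- Non-inferiority with unpooled variance: n = (1.96 + 1.2816)² × (0.09 + 0.21)/(0.20 + 0.075)² = 41.7, so 42. Power at 42 is Φ(0.275/√(0.30/42) - 1.96) = Φ(1.29) = 90.2%, the stated 90%.

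The last figure uses the Wald variance. Together with the half-width footnote, which fits a symmetric interval, it is consistent with a Wald reading of section 16.4 but does not state one.

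**Limits compared.**
- Wald: d - 1.96·√[p̂_T(1 - p̂_T)/n + p̂_R(1 - p̂_R)/n].
- Newcombe: d - √[(p̂_T - l_T)² + (u_R - p̂_R)²], where l_T and u_R are the lower and upper Wilson limits of the single rates.

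**Exact error.** For each n, all pairs of cured counts were enumerated with binomial probabilities at p_T = p_R - 0.075. The probabilities of the pairs whose lower limit exceeds -0.075 were then summed.

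| Reference / test rate | Wald, n = 42 / 45 / 50 | Newcombe, n = 42 / 45 / 50 |
|---|---|---|
| 60% / 52.5% | 2.9 / 3.0 / 3.1% | 2.8 / 3.0 / 3.1% |
| 70% / 62.5% | 2.7 / 2.6 / 2.7% | 2.5 / 2.6 / 2.7% |
| 80% / 72.5% | 2.9 / 2.7 / 2.7% | 2.5 / 2.6 / 2.7% |
| 90% / 82.5% | 3.1 / 3.3 / 2.9% | 2.2 / 2.2 / 2.3% |
| 95% / 87.5% | 3.9 / 4.6 / 3.4% | 1.7 / 2.0 / 2.0% |
| 97.5% / 90% | 7.1 / 6.4 / 4.5% | 1.3 / 1.3 / 1.8% |

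Over every n from 42 to 50, Wald gives 2.9-3.5%, 3.4-4.9% and 4.5-7.1% in the last three rows. The Farrington-Manning score test gives 2.2-2.6%, 1.7-2.4% and 1.3-2.1%.

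**Single results, 50 per arm.**
- 48 against 47 cured: d = 0.02. The Wald standard error is √(0.96·0.04/50 + 0.94·0.06/50) = 0.0435, so the limit is 0.02 - 0.0853 = -6.5%. For Newcombe, l_T = 0.8654 and u_R = 0.9794, so the limit is 0.02 - √(0.0946² + 0.0394²) = -8.2%.
- 49 against 49 cured: the Wald limit is 0 - 1.96 × 0.028 = -5.5%; Newcombe gives -8.7%.
- 47 against 45 cured: -6.6% and -7.7%.

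In all three, Wald declares non-inferiority while Newcombe and the score test do not.

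**The case against.** **The method is not stated.** A reader might infer that the protocol prescribes a Wald interval. It does not: that word is absent, and the footnote and power figure only fit such a reading. The unseen SAP may name another method under the same option. This stands, and it makes the error claim conditional. It does not remove the point, because section 16.4 has already chosen the procedure and option for a pass/fail test, and intervals obtainable under that option disagree on the same data.

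**The planned rates are not both near 90%.** A reader might infer that both arms will have only four or five failures. Section 16.5 expects 90% for the test product only. It sets the reference at 70% for non-inferiority and at 60% or 65% for superiority, which means roughly 13 to 20 reference failures among 42 to 50 patients. Even at the boundary with a 90% reference, the test arm is at 82.5%, or about 7 to 9 failures. This stands.

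**At the planned reference rates the remedy changes little.** With a reference of 60-80%, Wald runs at about 2.6-3.1% and Newcombe at about 2.5-3.1%, so neither holds 2.5% strictly. This stands too, and a general claim that the error rate is exceeded because of Wald would be too strong.

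**The consequence is limited.** Non-inferiority is a secondary objective, reached only if superiority fails, and the primary test against 70% does not use this interval. Correct. On the other side, the planned scenario, with the reference 20 points lower, is where the fallback is least likely to be needed. It is needed most when the arms are close.

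**Conclusion.** The point holds in conditional form. Section 16.4 ties the non-inferiority decision to an interval whose method it does not name. On the most literal reading, that interval exceeds the nominal one-sided 2.5% when cure rates are high. The excess is 0.4 to 0.8 points at a reference rate of 90%, for 42, 45 and 50 per arm. It becomes material only from about 95%, and the largest figure, 7.1%, needs a 97.5% reference rate and 42 per arm. Nothing in the protocol anticipates a reference rate that high, although 97.5% is the boundary value if the true test rate is exactly 90%.

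Assumptions: RISKDIFF run without a suboption gives Wald limits; patients are independent; per-protocol arms are equal with 42 to 50 patients. In four unequal splits (42/50, 50/42, 45/47, 48/44) the Wald error at a 90% reference was 2.7-3.7%. This is worth correcting, but it does not threaten the primary conclusion.

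**What to change.** In section 16.4, and in the same words in the SAP before database lock, name the interval for p_T - p_R: a score interval (Miettinen-Nurminen or Farrington-Manning) or Newcombe. Use it for both the non-inferiority decision and the reported two-sided 95% interval, so that the two cannot disagree. If the SAP already names such a method, bring section 16.4 into line with it.

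The work is one SAS option. The price is some power for non-inferiority (Wald to Newcombe or score):
- 90% against 70%: 94.5% to 94.3% with 50 per arm, and 90.9% to 89.3% with 42.
- 90% against 80%: 70.7% to 68.1% with 50 per arm, and 64.2% to 59.4% with 42.
- 90% against 90%: 25% to 20% with 50 per arm.

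The sample size and the primary analysis do not change.
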